**1. Determine the efficacy of an adaptive progressive VI reinforcement intervention for reducing cocaine use in the short- and long-term.** The hypothesis is that patients assigned to the adaptive progressive VI reinforcement intervention will achieve longer periods of abstinence than patients in standard care during the period reinforcement is in effect (24 weeks). We will also evaluate how well this reinforcement intervention maintains benefits throughout follow-up (18 months).

**2. Compare the relative efficacy of adaptive progressive VI reinforcement to a traditional reinforcement intervention.** Patients receiving adaptive progressive VI reinforcement are hypothesized to achieve greater during and post-treatment abstinence than those receiving traditional twice-weekly reinforcement.

Secondary and exploratory aims of the study are to:

**a. Evaluate relations between behavioral and measures of cognitive control and response to monetary rewards and treatment outcomes.** Patients with better cognitive control are expected to achieve longer durations of abstinence, regardless of treatment assignment. Patients who are more sensitive to monetary rewards are expected to achieve longer duration of abstinence, particularly when assigned to a reinforcement intervention. We also expect that sensitivity to monetary rewards and cognitive control may increase among those who are assigned to a reinforcement intervention, and that changes in these processes may mediate drug use outcomes.

**b. Assess the impact of reinforcement interventions on HIV risk and other outcomes.** Compared to SC, reinforcement interventions are expected to reduce high risk sexual behaviors that spread infectious diseases. Reinforcement interventions are also hypothesized to decrease psychiatric symptoms and improve quality of life. Both short-term and long-term effects will be examined. Gender effects will also be explored.

**c. Estimate costs and cost-effectiveness.** We will examine costs and cost-effectiveness of interventions and estimate conditions under which, and patients for whom, these interventions may be most cost-effective.

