Patients in this condition, as in Group A, will receive a study cell phone (or \$25/month toward their own cell phone service) if they maintain contact with research staff and submit samples when requested to do so. Because the reinforcement schedule for abstinence is set at twice weekly for 24 weeks, there is little reason to inform patients of reinforcement days throughout the study period. However, RAs will phone or text patients at the same frequency in this condition as in Groups A and C to inform them when "a sample is due to maintain cell phone service." If they fail to submit a sample when prompted, additional samples will be requested within the next week, as described in Group A. If two requested samples in a row are missed, then cell service will be discontinued. Reinstatement of cell service will be as described above.

In this manner, reinforcement for submission of negative samples is similar to that provided in traditional reinforcement interventions (pre-determined frequent urine testing). At the same time, prompting of urine sample submission (along with cell phone service for complying with submission) will be similar to other groups so that overall the same minimum number of samples should be obtained across conditions. In this manner, objective indicators of relapse to drug use will be obtained similarly across groups (see also Analyses).

Patients in this group can earn draws for providing negative samples in response to a cell phone prompt, and they may not have submitted these samples had they discontinued care in a traditional reinforcement intervention. In this sense, Group B is somewhat enhanced relative to traditional reinforcer interventions, and allows for a conservative test of Aim 2. Nevertheless, maximum draws per sample is only 1 when patients fail to submit negative samples twice weekly in this condition. Thus, the additional reinforcement for submission of samples by integrating cell phone prompted samples appears modest and unlikely to impact outcomes.

**C. Standard care + progressive VI reinforcement.** These patients receive standard care and earn draws with chances of winning prizes for submitting negative urine samples. However, relative to Group B, the frequency with which they are expected to submit samples to earn abstinence reinforcement decreases over time so long as they maintain abstinence. In the first phase, twice weekly samples are expected just like the other groups,

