**Data Analysis.** An important issue preceding analyses is to identify baseline differences between groups despite random assignment. Differences between groups that may be related to outcome (e.g., psychiatric diagnoses, dependence severity, clinic services received) will be used as covariates or fixed factors, as appropriate. Analysis will be conducted on an intent-to-treat basis, using all randomized patients, and both short-term (changes from baseline to month 6) and longer-term (throughout the 18-month follow-up) efficacy will be evaluated. The primary outcome is longest duration of cocaine abstinence, a continuous variable that can be transformed if needed. Groups will be compared using t-tests for normally distributed data, or ANCOVA if covariates are included. The design includes 3 treatment groups, allowing for analyses of two main effects.

Primary aim # 1 is to examine the efficacy of adaptive progressive VI reinforcement. We will compare those randomized to Group C vs Group A with respect to longest duration of abstinence during the 24-week intervention period and throughout the 18-month follow-up period.

Primary aim #2 is to assess if adaptive reinforcement improves duration of abstinence achieved relative to traditional reinforcement. We will compare those randomized to the two reinforcement conditions with respect to during treatment and long-term abstinence outcomes.

Secondary aims are to evaluate the impact of the interventions on other indices of stimulant and secondary drug use outcomes. Using the same contrasts above, we will compare groups with respect to: proportions of submitted and expected samples that test negative for stimulants and other drugs (alcohol, opioids, THC), and subjective reports of use (SUC % abstinent days). The first rely on objective indicators and such data will be available from all randomized patients. Subjective reports will supplement objective indices, and patients can be considered using if either index is positive. In terms of proportional data, missing samples will be considered missing (not impacting the denominator) in one analysis, and positive in another to consider the range of possibilities with respect to drug use outcomes. Because Group B has more expected samples (48) than the other groups ( $\geq 18$ ), proportional data for expected samples will rely upon the cell phone prompted samples ( $\geq 18$ ), designed to be similar across conditions, to conservatively test group differences.

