estimates and use real time, rather than scheduled time, of assessments. Two contrasts will be explored. One will evaluate Aim 1, assigning a contrast weight of +1 to patients in VI reinforcement and -1 to standard care. For aim 2, we will assign contrast weights of +1 to those receiving adaptive reinforcement and -1 to traditional reinforcement. Analyses will be conducted for both short- (BL to M6, with up to 4 data points/ patient: BL,M1,M3,M6) and long-term effects (BL through M18, with up to 8 data points/patient: BL,M1,3,6,9,12, 15,18). The model will include factors for group (using contrasts above), time, and the interaction of group by time. These analyses will ascertain whether the interventions impact areas of functioning beyond drug use.

Changes in other drug use over time can also be examined using urinalysis data. Means of  $\geq 18$  samples will be scheduled for collection over 24 weeks, and  $\geq 22$  samples through the M18 follow-up. Samples will be coded as positive for any illicit drug or negative for all substances. HLM using MIXOR (Hedeker, 1996), an HLM program for dichotomous measures, will examine group changes over time, using contrasts above.

Moderators of effects will be explored. To date, we have investigated gender as a moderator of effects but never observed gender effects on drug use outcomes in reinforcement studies (e.g., Petry et al., 2005ac, 2006a,2010b,2011a,2012a), perhaps in part because we provide highly desired prizes for both men and women (Petry, 2012). Nonetheless, effects of gender will be explored, as will interactions between gender, treatment condition, and other characteristics that may impact outcomes. Although we do not anticipate gender differences in main outcomes, we expect to find gender-specific HIV risk behaviors (Barry et al., 2008; Rash & Petry, 2009). We have also found that women show greater heritability of impulsive responding on cognitive tasks than men (Petry et al., 2002) and women with addictive disorders and ASPD are particularly impulsive (Andrade et al., under review).

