For cost and feasibility issues, the fMRI study is limited to patients in groups most likely to show treatment differences, Groups A and C. This design most cost-effectively addresses the issue of if, and how, the availability of monetary based reinforcers alter brain functioning. Based on our earlier work (Devito et al., 2012; Kober et al., 2010) and pilot data, we estimate a medium effect size for changes in regions such as VS and PFC regions. Thirty participants per group is sufficient to determine correlations of  $r \geq .30$  between neural activity in Stroop and MID task and outcome variables. We estimate 25 participants post treatment will be sufficient to assess treatment-related changes in neural activity over time (see Devito et al., 2012).

If effects of reinforcement interventions are moderated by cognitive control, future studies may target these interventions toward patients based on cognitive functioning. As reinforcers add known costs, being able to determine those who will be most positively affected will help direct scarce resources toward patients most likely to benefit. If cognitive function mediates outcomes, future research may refine and test therapies that reduce impulsive choices, and improve cognitive flexibility, inhibition and/or control (Bickel et al., 2011). Combining reinforcement with an intervention that improves cognitive control may result in even more durable effects, which may reduce personal-- and societal—harms related to drug abuse.

**Economic Evaluation.** If primary hypotheses are supported, we will conduct cost-benefit analyses. These interventions can be costly, even when reinforcers are relatively modest. Not only must costs of reinforcers be included, but so must administration costs, which include staff time for managing and delivering reinforcers. Despite costs, these interventions may provide benefits to (1) clinics in terms of enhanced reimbursements (Lott & Jencius, 2009), and (2) society in terms of reductions in healthcare services (hospitalizations, ER visits) and criminal justice system costs, and improvements in workplace productivity (Petry et al., in press c). Using data from the PAC-SAT, this study will determine the net benefit of adding reinforcers, from both clinic and societal perspectives. It will also estimate costs of each week of abstinence attributable to the reinforcement conditions.

- a. Comprehensive administrative costs of interventions will be quantified (Olmstead et al., 2007abc;

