Calculation of net benefits. First, resource utilization and cost data will be used to estimate the average net benefit (i.e., benefits – costs) per patient in each intervention from clinic and societal perspectives (Drummond et al., 2005; Zarkin et al., 2008). Second, average net benefits, and confidence intervals around estimates, will be calculated by subtracting average net benefit of adaptive reinforcement from standard care, or adaptive from traditional reinforcement. Finally, sensitivity analyses (Olmstead et al., 2007a; Drummond et al., 2005) will determine the robustness of the net benefit to alternative assumptions about a variety of cost parameters (e.g., unit costs of services, reimbursements received). If reimbursements rise by maximizing the number of patients attending groups via reinforcement treatment, net benefits are higher as shown by Lott and Jencius (2009).

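### No planned contrast compares traditional reinforcement (Group B) with standard care (Group A), so the secondary hypothesis about reinforcement versus standard care is tested only for the adaptive arm (Group C)

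*Combined protocol and SAP*

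**What the plan says.** The Data Analysis paragraph (Methods, under Design considerations) states: "The design includes 3 treatment groups, allowing for analyses of two main effects". The first is "We will compare those randomized to Group C vs Group A with respect to longest duration of abstinence during the 24-week intervention period", and also through the 18-month follow-up. The second is "We will compare those randomized to the two reinforcement conditions with respect to during treatment and long-term abstinence outcomes". Secondary drug-use outcomes reuse these two.

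For psychosocial functioning, quality of life and HIV risk, the Secondary aims paragraph says "Two contrasts will be explored". It codes them as C (+1) against A (-1) and C (+1) against B (-1). The urinalysis mixed model uses the same pair. Under Calculation of net benefits, the differences are "calculated by subtracting average net benefit of adaptive reinforcement from standard care, or adaptive from traditional reinforcement".

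The hypotheses are broader. Specific aims, aim b: "Compared to SC, reinforcement interventions are expected to reduce high risk sexual behaviors that spread infectious diseases". The next sentence extends the expectation to psychiatric symptoms and quality of life, again for reinforcement interventions in the plural. The Secondary aims paragraph likewise describes its purpose as finding out whether reinforcement improves these outcomes.

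**The concern.** The secondary hypothesis covers two reinforcement arms, but the coded contrasts compare only one of them with standard care. An analyst who follows the plan exactly will report nothing on whether traditional reinforcement changed HIV risk, psychiatric symptoms or quality of life relative to standard care.

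The same omission leaves Aim 2 without a supporting check on its comparator. The Methods section says that "Group B is somewhat enhanced relative to traditional reinforcer interventions, and allows for a conservative test of Aim 2", because draws can also be earned on samples prompted by phone. Group B here is therefore a somewhat modified version of the intervention, run for 24 weeks, where the completed cocaine studies described in Preliminary studies ran for 12. Whether it beat standard care in these clinics can be estimated from the randomised arms, but the plan does not ask for the estimate. If the contrast is added only after the results are seen, it becomes a post hoc choice.

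**Working it through.** **1. Contrasts against hypotheses.**

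| Analysis | C v A | C v B | B v A |
|---|---|---|---|
| Longest duration of abstinence (primary) | yes | yes | no |
| Secondary drug use | yes | yes | no |
| Mixed models: psychosocial, quality of life, HIV risk | yes | yes | no |
| Urinalysis mixed model | yes | yes | no |
| Net-benefit differences | yes | yes | no |

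A pooled B+C v A contrast is not specified either. Treatment condition is a predictor in the exploratory regressions, so A and B are modelled together there, but no B v A coding or test is defined.

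**2. The plan's own sample sizes.** Inputs from Power analyses for primary aims: alpha .05 (sidedness not stated), power 0.80, d = 0.46 for Aim 1 and d = 0.35 for Aim 2. Per-group n = 2(z_alpha + z_power)²/d².

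- d = 0.46: one-sided 2(1.645 + 0.842)²/0.2116, giving 59 (60 by the exact t). Two-sided 2(1.960 + 0.842)²/0.2116, giving 75 (76). The stated 60 is reproduced one-sided only.
- d = 0.35: one-sided 101 (102); two-sided 129 (130). The stated 110 is reproduced by neither.

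The total does add up: 60 + 110 + 110 = 280. No figure is given for B v A.

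**3. B v A at the planned allocation (60 v 110).** In SD units, SE = √(1/60 + 1/110) = 0.160. Two-sided power is approximately Φ(d/SE − 1.960).

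| d | Normal approximation | Exact noncentral t |
|---|---|---|
| 0.35 | 58.7% | 58.3% |
| 0.46 | 81.8% | 81.3% |
| 0.60 | 96.2% | 96.1% |

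The smallest d at 80% power is (1.960 + 0.842) × 0.160 = 0.45, and the 95% CI half-width is 1.96 × 0.160 = 0.31 SD. C v A has the same arm sizes and so the same power.

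**4. What the two planned contrasts already imply.** For unadjusted means, B − A = (C − A) − (C − B), so the point estimate can be recovered. The interval cannot be got by simply adding the two variances, because both contrasts share arm C. The variance is (1/110 + 1/60) + 2/110 − 2(1/110) = 1/110 + 1/60, the direct contrast's own.

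**5. Patterns of result.**

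- C beats A and C beats B: both primary aims are answered. Only the description of B as an effective comparator lacks direct support.
- C beats A, C v B null: C worked, and B's own status is untested. The C v B half-width is 1.96 × √(2/110) = 0.26 SD and no equivalence margin is set, so the null does not show similarity. Two-sided power for C v B at d = 0.35 is about 73%, so this pattern is quite possible even if the assumed difference exists.
- C v A null, C v B null: no planned contrast shows whether the comparator had any effect in this trial.

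**The case against.** The strongest reply is that the omission is a reasoned choice. Both primary hypotheses concern only the adaptive arm, and the plan treats traditional reinforcement against standard care as largely established, so it spends its primary comparisons on the new intervention. That stands: B v A need not be primary. It does not explain why aim b is worded for both arms.

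A reader might infer more than the documents support, in four ways.

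- *That Aim 2 cannot be interpreted.* C better than B is a valid randomised estimate and answers Aim 2 as written, and C v A tests directly whether C worked.
- *That Group B probably fails.* The plan reports that 33% of the longest-reinforcement arm completed 12 weeks of treatment. But 82.1% of patients kept submitting samples after leaving treatment, and the 12-week arm had longer abstinence than patients never reinforced (p < .05). A 24-week pilot arm reached 12.4 ± 8.5 weeks against 7.8 ± 6.8 in standard care: 4.6/√((8.5² + 6.8²)/2) ≈ 0.60, if the arms were of equal size. Those were alcohol-dependent patients, so the support is indirect. The Group B text also treats its prompted samples as a modest addition that strengthens the arm.
- *That B's cost per abstinent week cannot be obtained.* The plan says "It will also estimate costs of each week of abstinence attributable to the reinforcement conditions", first estimates average net benefit in each intervention, and does not restrict the cost-effectiveness ratio to comparisons involving C. Only the listed net-benefit differences omit B v A.
- *That A and B never meet in an analysis.* They do, in the exploratory regressions, though without a defined test.

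**Conclusion.** The concern holds as a gap in the secondary analyses and in the context for Aim 2. It is not a flaw in either primary test. Aim b's comparison with standard care is untested for Group B whatever the results, and B's efficacy in this trial goes unexamined in the patterns where a reader would most want it: C v B null alone, or both contrasts null.

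The planned arms can fill the gap: about 81% power at d = 0.46 and 96% at d = 0.60, but only 58% at d = 0.35, with an interval of ±0.31 SD. These figures assume a two-sided .05 t-test, equal variances and complete data on all 170 patients. The aim b outcomes will have missing values and are analysed by mixed models, so their power will differ.

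The modest power at smaller effects limits how the contrast may be used. A non-significant B v A would not show that B failed, and a favourable B v A interval would not make a non-significant C v B into evidence of similarity.

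**What to change.** Prespecify B v A as a supportive secondary contrast for longest duration of abstinence and for the aim b outcomes (HIV risk, psychiatric symptoms, quality of life), in the models already planned. Report it with a 95% confidence interval, outside the primary alpha. Splitting alpha over three contrasts instead would cut power at d = 0.46 to about 68% (.05/3, normal approximation). Add the traditional-minus-standard-care difference, with its interval, to the net-benefit comparisons.

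State that B v A gives context for reading Aim 2 and is not a condition for claiming it. State also that non-significance in B v A or C v B will not be read as failure or similarity respectively.

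Two lesser options would mend aim b only. Rewording it to the adaptive arm removes the mismatch. A pooled B+C v A contrast (220 v 60, about 88% power at d = 0.46) tests reinforcement in general. Neither shows whether B itself worked.

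Cost: no extra patients, visits or data; one more secondary contrast to report per outcome, over both the short- and long-term windows.

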To ensure contact and submission of samples on requested days, patients will receive a study cell phone (allowing unlimited calls and texting) as long as they do not miss more than one requested sample in a row. If a patient fails to submit a sample on a testing day, the RA will phone the patient that afternoon/evening and remind him/her that if s/he fails to provide a sample the *next* selected testing day, the phone will be turned off. After a missed sample, the next two test days will be prompted for sample submission. For example, if a patient failed to submit a sample when requested on a Mon, that patient would be prompted for another sample that Thur, and the following Mon. If the patient missed the Thur sample (or any two prompted samples in a row), cell service would be discontinued. The goal is to obtain on average  $\geq 18$  samples from patients across 24 weeks and equivalent samples relative to Group C, so that objective indices of drug use will be available similarly across conditions. (To accommodate for the potential of higher test days that may occur in Group C patients who relapse, additional test days will be randomly selected based on running averages of samples obtained from patients in the adaptive condition; [name] has developed and maintained programs to automate sample selection days in ongoing and pilot trials). This system encourages submission of samples to accurately and consistently gauge drug use, without being unduly burdensome.

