**B. Standard care + twice weekly reinforcement for abstinence:** Patients assigned to this condition will receive standard care and urine sample monitoring as above. As in Group A, patients will receive \$2 per requested sample submitted, plus a \$20 bonus if they submit all requested samples in a four week period (regardless of results). In the case of an excused absence, patients can come in the next day to submit a sample and still be eligible for the \$20 bonus. These patients will also draw from an urn and have a chance to win prizes each day they provide a stimulant negative urine sample according to their twice-weekly testing schedule. For the first stimulant negative sample provided, they will earn one draw from a prize bowl, and the number of draws earned will increase by one for each consecutive negative sample submitted up to a maximum of 5 draws per negative sample (after 3 weeks of abstinence). If ever a patient fails to leave any of their twice weekly samples or submits a positive sample, draws earned the next time they leave a negative sample will reset to 1, and then escalate as before. Excused absences (medical or court appointment arranged in advance with therapist, and verified emergencies, e.g., car broke down with tow receipt) will not reset draws.

The urn will contain 500 cards, and 50% of them will be winning cards. Of these, 204 will be small prizes (patient's choice of \$1 coupons, toiletries, food items, or bus tokens); 45 will be large prizes, worth up to \$20 in value (choice of CDs, gift cards, watches), and one will be a jumbo prize up to \$100 (choice of stereo, TV, or five larges). Cards are replaced after each draw, so that chances of winning remain constant. A variety of prizes will be kept in a locked cabinet, and when patients win they chose a prize from that category. This schedule provides similar probabilities and magnitudes of prizes as our prior studies (Petry et al., 2004,2005abc,2006a, 2007a,2011a,2012abc). Patients have an expected maximum average earning of 229 draws (mean expected earnings of \$460 in prizes) if they submit all 48 negative urine samples over 24 weeks.

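### The plan corrects for Group B's heavier testing only in a secondary outcome; the primary 24-week longest duration of abstinence has no scoring rule and can carry a testing-frequency artefact

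*Combined protocol and SAP*

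**What the plan says.** The Data Analysis section states: "The primary outcome is longest duration of cocaine abstinence, a continuous variable that can be transformed if needed". Group C is compared with Group A (Aim 1) and with Group B (Aim 2) by t-test or ANCOVA, over the 24 weeks and through 18 months.

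Two safeguards follow, both in the paragraph on secondary aims. On missed samples: "In terms of proportional data, missing samples will be considered missing (not impacting the denominator) in one analysis, and positive in another". On unequal testing (48 expected samples in Group B, at least 18 elsewhere): "proportional data for expected samples will rely upon the cell phone prompted samples". On self-report the wording is permissive: "patients can be considered using if either index is positive".

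The intervention sections set the testing. Group B's full prize earnings are reached by patients "if they submit all 48 negative urine samples over 24 weeks". Prompting is meant to be equal. For Group A, "additional test days will be randomly selected based on running averages of samples obtained from patients in the adaptive condition"; Group B is to be contacted as often as the other groups; and Data Quality Control makes the project director responsible for equal prompts. After a miss, "After a missed sample, the next two test days will be prompted for sample submission", and "If the patient missed the Thur sample (or any two prompted samples in a row), cell service would be discontinued".

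None of these sentences says which samples score the primary outcome. The reset rules in sections B and C govern prize draws. The Preliminary studies section reports duration of abstinence in weeks, scored from samples alone and also with self-reports, but chooses neither for this trial.

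**The concern.** An observed run of abstinence depends on how often one looks. An arm tested twice a week for 24 weeks has more occasions to show a positive or miss a sample than an arm whose testing thins out as abstinence continues. The plan sees this for the proportions and repairs it there. It does not carry the repair to the primary outcome, where the same imbalance acts.

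The authors' own experience shows that such choices matter. In their ongoing trial (Preliminary studies), group differences in the percentage of negative samples appeared or vanished according to whether expected or submitted samples formed the denominator.

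At stake is the 24-week Aim 2 contrast, Group C against Group B, powered for d = 0.35. If the rule is chosen after results are seen by group, part or all of an effect of that size could come from the choice of samples and the treatment of misses.

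**Working it through.** **1. The plan's sample counts.** Group B: 2 x 24 = 48. Group C, if every sample is negative (section C): 2 x 3 + 1 x 6 + 6/2 + 9/3 = 6 + 6 + 3 + 3 = 18. Both agree with Data Analysis. The figure of 18 applies only to Group C patients who stay abstinent, because testing rises after a positive or a miss. The Human Subjects section tells all participants to expect 15 to 35 requests in weeks 4-24. With six in weeks 1-3, that is 6 + 15 = 21 to 6 + 35 = 41.

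**2. A fully abstinent patient.** Suppose each expected sample is missed with probability m and every miss ends a run. Then P(unbroken 24 weeks) = (1 - m)^n.

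| m (assumed) | Group B, n = 48 | Group C, n = 18 |
|---|---|---|
| 5% | 0.95^48 = 8.5% | 0.95^18 = 39.7% |
| 10% | 0.90^48 = 0.6% | 0.90^18 = 15.0% |

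The two patients behave identically; only the schedule differs.

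**3. Null simulations.** Drug use was generated by the same process in each arm, and d = (mean C - mean B)/pooled SD. Taken from the documents: the two schedules, including Group C's reset; 30-50% of patients never becoming abstinent (Research Strategy), used as a share of persistent users; and a mean of 10 use days a month (Design considerations), applied to those users. Assumed: lapse patterns in the rest, a 3-day urine detection window and the miss rates. The wider set also covers populations with few persistent users.

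All 48 Group B samples scored, calendar time:

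| Inputs | No misses | 5% missed, every miss breaks a run |
|---|---|---|
| 30-50% persistent users (window 2-4 days) | -0.11 to 0.33 | 0.14 to 0.57 |
| Wider set | -0.20 to 0.65 | 0.11 to 0.97 |

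A different use model (use on 4-14% of days) gave -0.17 to 0.29 with no misses or misses ignored, and 0.31 to 0.77 with 3-15% missed and every miss breaking a run. With misses ignored, the run boundary matters: the -0.17 arises when a run is credited from first to last negative, the 0.29 when it is credited from one break to the next.

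For scale, the pilot SDs of 6.8 to 8.5 weeks (Preliminary studies, an alcohol trial) make d = 0.35 equal to 0.35 x 6.8 = 2.4 up to 0.35 x 8.5 = 3.0 weeks.

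**4. Self-report.** In the 30-50% set, if half of use days are reported, the no-miss range becomes -0.15 to 0.13 and the 5% range 0.11 to 0.36. In the different use model, complete and honest daily report with misses ignored leaves |d| at or below 0.01.

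**5. Prompted samples only, prompts matched to Group C, 5% missed in every arm.** d is 0.02 to 0.13 if every miss breaks a run, and -0.10 to 0.01 if only two consecutive misses do.

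**6. Unequal submission.** Preliminary studies report mean samples obtained of 10.5 under standard care and 14.8 under 12 weeks of reinforcement. With an assumed 15% missed in Group C and 30% in the comparator, and no true difference, the two-miss rule gives d of about 0.35 to 0.81. Ignoring misses gives about -0.05 to 0.03.

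**The case against.** The plan does not ignore the problem. It matches prompts across arms so that objective data are comparable, gives one person responsibility for that, collects a cocaine-use calendar in every arm through the Timeline Follow-back, and argues in Design considerations that typical use would be caught even when testing is sparse. One may fairly suspect that the authors meant to score the primary outcome from prompted samples. That intention is plausible and lowers the severity, but no sentence states it, and the permissive line on self-report does not settle it.

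The simulated sizes also rest on chosen inputs. With 30-50% persistent users, Group C averaged 30-39 tests, whereas Human Subjects estimates 18-23 samples per patient. A rebuild gave 56-75% negative samples in Group B, against more than 80% in the authors' ongoing trial. This objection stands against reading any single value as a forecast. It does not remove the artefact: with 0-10% persistent users the no-miss values ran from -0.15 to 0.67.

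Three stronger readings are tempting and unsupported:

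- A reader might infer that Aim 2 has a calculable false-positive rate. The documents fix neither the rule nor the use and miss patterns, so no such rate belongs to the plan.
- A reader might infer a large reversal in Group B's favour if consecutive negatives were counted. The documents express duration of abstinence in weeks, so that scoring is not suggested.
- A reader might infer that prompted-only scoring makes the comparison neutral. That needs equal submission across arms, which the authors hope for but cannot guarantee.

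**Conclusion.** The concern holds for the 24-week primary outcome. No sample set, missed-sample rule or run boundary is stated, and the correction for 48 against at least 18 expected samples stops at a secondary outcome. Scoring all of Group B's samples would make the measure depend on arm. Under identical drug use the illustrative range is d of about -0.2 to 0.65 with no misses and about 0.1 to 1.0 at 5% missed if every miss breaks a run, mostly in favour of Group C. The design effect of 0.35 can be passed without any misses when few patients use persistently.

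These ranges depend on the assumed use patterns, 3-day window and miss rates. Self-report would shrink them if the plan committed to using it. Nothing is claimed for assessments after month 6. This should be fixed, but it is not a fatal flaw, because the plan already contains the remedy and needs only to extend it.

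**What to change.** Extend the Data Analysis safeguard to the primary outcome in one paragraph, fixed before outcomes are compared by group:

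- Score 24-week longest duration of abstinence in calendar time, by one rule for all arms, from prompted samples plus the common twice-weekly tests of weeks 1-3.
- End a run at a positive sample or a self-reported cocaine-use day, and state how time at each end of a run is credited.
- As for the proportions, report the outcome with missed samples ignored and with missed samples treated as positive, and name in advance which is primary.
- Tabulate achieved prompts and submission rates by arm.
- Give the result from all of Group B's samples as a sensitivity analysis.

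This needs no new data, but it has costs. Group B's unprompted samples, including any positives, leave the primary score unless self-report captures the use. Ignoring misses can hide use. Any rule in which misses end a run is biased when submission differs by arm, so the report should not claim a near-zero residual for C against B or C against A.
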